10.5 Does the plan describe methods for adjusting for				

Section 10: Analysis plan	Yes	No	N/A	Page Number(s)
confounding?				
10.6 Does the plan describe methods addressing effect modification?				

Comments:

--

Section 11: Data management and quality control	Yes	No	N/A	Page Number(s)
11.1 Is information provided on the management of missing data?				20
11.2 Does the protocol provide information on data storage? (e.g. software and IT environment, database maintenance and anti-fraud protection, archiving)				19
11.3 Are methods of quality assurance described?				20
11.4 Does the protocol describe possible quality issues related to the data source(s)?				19
11.5 Is there a system in place for independent review of study results?				

Comments:

--

Section 12: Limitations	Yes	No	N/A	Page Number(s)
12.1 Does the protocol discuss:				
12.1.1 Selection biases?				21
12.1.2 Information biases?				21
(e.g. anticipated direction and magnitude of such biases, validation sub-study, use of validation and external data, analytical methods)				
12.2 Does the protocol discuss study feasibility? (e.g. sample size, anticipated exposure, duration of follow-up in a cohort study, patient recruitment)				21
12.3 Does the protocol address other limitations?				21

Comments:

--

Section 13: Ethical issues	Yes	No	N/A	Page Number(s)
13.1 Have requirements of Ethics Committee/Institutional Review Board approval been described?				22
13.2 Has any outcome of an ethical review procedure been addressed?				
13.3 Have data protection requirements been described?				22

Comments:

--

Section 14: Amendments and deviations	Yes	No	N/A	Page Number(s)
14.1 Does the protocol include a section to document future amendments and deviations?				12

Comments:

--

Section 15: Plans for communication of study results	Yes	No	N/A	Page Number(s)
15.1 Are plans described for communicating study results (e.g. to regulatory authorities)?				24
15.2 Are plans described for disseminating study results externally, including publication?				24

Comments:

--

Name of the main author of the protocol: _____

Date: / /

Signature: _____

Annex 3.

Additional Information

Patient information card:35
Prescribers' Checklist:37
Physician Questionnaire **Error! Bookmark not defined.**

Patient information card:

Indication for which Diane-35 is prescribed:

Treatment of moderate to severe acne related to androgen sensitivity (with or without seborrhoea) and/or hirsutism, in women of reproductive age.

For the treatment of acne, Diane-35 should only be used after topical therapy or systemic antibiotic treatments have failed.

Since Diane-35 is also a hormonal contraceptive, it should not be used in combination with other hormonal contraceptives.

IMPORTANT INFORMATION ABOUT [PRODUCT NAME] AND RISK OF BLOOD CLOTS

All estrogen-progestagen combination products like [product name] increase the rare but important risk of having a blood clot. The overall risk of a blood clot is small but clots can be serious and may in very rare cases even be fatal.

It is very important that you recognise when you might be at greater risk of a blood clot, what signs and symptoms you need to look out for and what action you need to take.

In which situations is the risk of a blood clot highest?

- in the first year of using [product name] (including if you are re-starting use after a break of 1 month or more)
- if you are very overweight (body mass index over 30 kg/m²)
- if you are older than 35 years
- if you have a close family member who has had a blood clot at a relatively young age (e.g. below 50)
- if you have given birth in the previous few weeks

If you smoke and are over 35 years old you are strongly advised to stop smoking or use a non-hormonal treatment for your acne and/or hirsutism.

Seek medical attention immediately if you experience any of the following symptoms:

- Severe pain or swelling in either of your legs that may be accompanied by tenderness, warmth or changes in the skin colour such as turning pale, red or blue. You may be experiencing a **deep vein thrombosis**.
- Sudden unexplained breathlessness or rapid breathing; severe pain in the chest which may increase with deep breathing; sudden cough without an obvious cause (which may bring up blood); You may be experiencing a serious complication of deep vein thrombosis called a **pulmonary embolism**. This occurs if the blood clot travels from the leg to the lung.
- Chest pain, often acute, but sometimes just discomfort, pressure, heaviness, upper body discomfort radiating to the back, jaw, throat, arm together with a feeling of fullness associated with indigestion or choking, sweating, nausea, vomiting or dizziness. You may be experiencing a **heart attack**
- Face, arm or leg weakness or numbness, especially on one side of the body; trouble speaking or understanding; sudden confusion; sudden loss of vision or blurred vision; severe headache/migraine that is worse than normal. You may be experiencing a **stroke**.

Watch out for symptoms of a blood clot, especially if you have:

- Just had an operation
- been off your feet for a long time (e.g. because of an injury or illness, or if your leg is in a cast)
- a long journey (e.g. a long-haul flight)

Remember to tell your doctor, nurse or surgeon that you are taking [product name] if you:

- Are due to or have had surgery
- Are asked by a healthcare professional if you are taking any medication

For further information please read the accompanying Patient Information Leaflet or go to [NCA web address].

If you suspect you have an undesirable effect associated with the use of your medication, you can report it to a Healthcare professional.

Prescribers' Checklist:

CHECKLIST FOR PRESCRIBERS – cyproterone/ethinylestradiol [Product name]

Please use this checklist in conjunction with the Summary of Product Characteristics and at regular intervals.

Indication for which Diane-35 is prescribed:

Treatment of moderate to severe acne related to androgen sensitivity (with or without seborrhoea) and/or hirsutism, in women of reproductive age.

For the treatment of acne, Diane-35 should only be used after topical therapy or systemic antibiotic treatments have failed.

Since Diane-35 is also a hormonal contraceptive, it should not be used in combination with other hormonal contraceptives.

- Thromboembolism (e.g. deep vein thrombosis, pulmonary embolism, heart attack and stroke) is a rare but important risk with use of cyproterone/ethinylestradiol [Product name].
- A woman's risk will also depend on her baseline risk of thromboembolism. The decision to use cyproterone/ethinylestradiol [Product name] should therefore take into consideration the contraindications and a woman's risk factors, particularly those for thromboembolism – see boxes below and the Summary of Product Characteristics.
- The risk of a thromboembolism with cyproterone/ethinylestradiol [Product name] is higher:
 - during the first year of use
 - when re-starting use after an intake break of 1 month or more.
- The decision to use cyproterone/ethinylestradiol [Product name] should be taken only after a discussion with the woman to ensure she understands
 - the effect of any intrinsic risk factors on her risk of thrombosis
 - the risk of thromboembolism with [Product name]
 - that she must be alert for signs and symptoms of a thrombosis

Please be reminded to consider the possibility of a thromboembolic event in healthy girls/women also in case of non-distinct, unexplained complaints like pain in the leg, cough/dyspnoea, or headache.

Do not prescribe cyproterone/ethinylestradiol [Product name] if you tick any of the boxes in this section. Does the woman have:

	Concomitant use with another hormonal contraceptive?
	Current or personal history of a thromboembolic event e.g. deep vein thrombosis, pulmonary embolism, heart attack, stroke, transient ischaemic attack, angina pectoris?
	Knowledge of predisposition for a blood clotting disorder personally?
	History of migraine with aura?
	Diabetes mellitus with vascular complications?
	Very high blood pressure eg systolic ≥ 160 or diastolic ≥ 100 mm Hg?

	Very high blood lipids?
	Major surgery or a period of prolonged immobilisation coming up? If so, advise the patient to stop using Diane-35 and to use a non-hormonal treatment for their skin condition and if necessary a non-hormonal method of contraception for at least 4 weeks beforehand and two weeks after full ambulation* .

Discuss the suitability of cyproterone/ethinylestradiol [Product name] with the woman if you tick any of the boxes in this section:

	Is her BMI over 30 kg/m ² ?
	Is she aged over 35 years?
	Is she a smoker? If yes and also over the age of 35 she should be strongly advised to stop smoking or use a non-hormonal treatment for her acne and/or hirsutism.
	Does she have high blood pressure eg systolic 140-159 or diastolic 90-99mm Hg?
	Does she have a close relative (e.g. parent or sibling) who has had a thromboembolic event (see above list) at a young age (e.g before 50)?
	Does she or someone in her immediate family have high blood lipids?
	Does she get migraines?
	Does she have a cardiovascular condition such as atrial fibrillation, arrhythmia, coronary heart disease, cardiac valve disease?
	Does she have diabetes mellitus?
	Has she given birth in the last few weeks?
	Does she have any other medical conditions that might increase the risk of thrombosis (eg. cancer, systemic lupus erythematosus, sickle cell disease, Crohn's disease, ulcerative colitis, haemolytic uraemic syndrome)?
	Is she taking any other medicines that can increase the risk of thrombosis (e.g. corticosteroids, neuroleptics, antipsychotics, antidepressants, chemotherapy etc)?

More than one risk factor may mean cyproterone/ethinylestradiol [Product name] should not be used.

Don't forget, a woman's risk factors may change over time and might need to be revisited at regular intervals.

Please make sure your patient understands that she should tell a healthcare professional she is taking cyproterone/ethinylestradiol [Product name] if she:

- Needs an operation
- Needs to have a period of prolonged immobilisation (eg because of an injury or illness, or if her leg is in a cast)
- In these situations it would be best to discuss to discontinue cyproterone/ethinylestradiol [Product name] until the risk returns to normal.

Please also tell your patient that the risk of a blood clot is increased if she:

- Travels for extended periods (e.g. on long-haul flights)
- Develops one or more of the above risk factors for cyproterone/ethinylestradiol [Product name].
- Has given birth within the last few weeks

- In these situations your patients should be particularly alert for any signs and symptoms of a thromboembolism.

Please **advise your patient to tell you** if any of the above situations change or get much worse.

Please strongly encourage women to read the Patient Information Leaflet that accompanies each pack of [product name]. This includes the symptoms of blood clots that she must watch out for.

Please report any adverse events suspected to be caused by cyproterone/ethinylestradiol [Product name] to the [company] or the [NCA]

Diane-35 (cyproterone acetate 2 mg/ethinylestradiol 35 µg) Risk Minimisation Plan Evaluation

Physician Questionnaire

Physician Questionnaire

This questionnaire is designed to gain a better understanding of prescribers' knowledge and understanding of key safety information for Diane-35 and its generics. This questionnaire will be used to determine if the educational materials for Diane-35 and its generics are understood accurately and whether these materials could be improved.

Q8. Diane-35 and its generics are indicated for the following purposes. Tick Yes, No, or I don't know for each purpose listed.

Purpose	Yes	No	I don't know
For the treatment of mild acne related to androgen sensitivity (with or without seborrhoea) in women of reproductive age			
For the treatment of moderate to severe acne related to androgen sensitivity (with or without seborrhoea) in women of reproductive age	 *		
For contraception only			
For the treatment of androgenic alopecia in women of reproductive age			
For the treatment of hirsutism in women of reproductive age	 *		

Q9. For the treatment of acne, Diane-35 and its generics should be used only after topical therapy or systemic antibiotic treatments have failed.

- True*
- False
- I don't know

Q10. Patients should be informed that when taking Diane-35 or its generics that the risk of thrombosis is highest during which time periods?

Tick Yes, No, or I don't know for each circumstance listed.

Circumstance	Yes	No	I don't know
During the first year of use	 *		
After using the medication for more than 1 year			
When re-starting use after a break of 1 month or more	 *		

Q11. When taking Diane-35 or its generics, the risk of a thrombosis is highest with which of the following risk factors?

Tick Yes, No, or I don't know for each risk factor listed.

Risk Factors	Yes	No	I don't know
If the patient is very overweight (body mass index greater than 30 kg/m ²)	 *		
If the patient is 35 years of age or younger			
If the patient is older than 35 years of age	 *		
If the patient has a close family member who has had a thrombosis at a relatively young age (e.g., younger than 50 years of age)	 *		
If the patient smokes and is older than 35 years of age	 *		
If the patient has a family history of hypertension and/or dyslipidemia			

Q12. Patients taking Diane-35 or its generics should watch out for symptoms of a thrombosis in which of the following situations?

Tick Yes, No, or I don't know for each situation listed.

Situation	Yes	No	I don't know
Just after having an operation	 *		
When participating in exercise activities such as short-distance running or jogging			
When the patient has been off her feet for a long time (e.g., because of an injury or illness or if her leg is in a cast)	 *		
During or after a long journey (e.g., a long flight)	 *		
When initiating treatment with Diane-35 or its generics within a few weeks after having a baby	 *		

Q13. What instructions should patients taking Diane-35 or its generics receive regarding the potential need for a major surgery, or occurrence of an

injury or condition that may also require a period of prolonged immobilisation?

Tick Yes, No, or I don't know for each instruction listed.

Instruction	Yes	No	I don't know
Tell their doctor, nurse, or surgeon that they are taking Diane-35 or its generics	 *		
Stop using Diane-35 or its generics for at least 2 weeks in advance of a major surgery or a required period of prolonged immobilisation			
Stop using Diane-35 or its generics for at least 4 weeks in advance of a major surgery or a required period of prolonged immobilisation	 *		
Use a non-hormonal treatment for their skin condition and, if necessary , a non-hormonal method of contraception during this time	 *		
Resume treatment with Diane-35 or its generics at 1 week after complete remobilisation			
Resume treatment with Diane-35 or its generics at 2 weeks or later after complete remobilisation	 *		

Q14. Diane-35 and its generics are contraindicated in which of the following patient populations?

Tick Yes, No, or I don't know for each patient population listed.

Population	Yes	No	I don't know
Patients who are currently using another hormonal contraceptive	 *		
Patients who have a current or history of a thromboembolic event (e.g., deep vein thrombosis, pulmonary embolism, myocardial infarction, cerebrovascular accident, transient ischaemic attack, angina pectoris)	 *		
Patients with a history of childhood asthma			
Patients who have knowledge of a predisposition for a blood clotting disorder	 *		
Patients with a history of migraine with aura	 *		
Patients with moderate anaemia			
Patients with diabetes mellitus and concurrent vascular complications	 *		
Patients with hypertension (e.g., systolic \geq 160 or diastolic \geq 100 mm Hg)	 *		
Patients with dyslipidemia	 *		
Patients who have had a recent major surgery	 *		
Patients who are experiencing or expected to experience a period of prolonged immobilisation	 *		

Q15. Which of the following risk factors for the development of thrombosis should be considered prior to prescribing Diane-35 and its generics? Tick Yes, No, or I don't know for each risk factor listed.

Risk Factor	Yes	No	I don't know
Body mass index over 30 kg/m ²	 *		
Age greater than 35 years	 *		
Smoker	 *		
Hypertension (i.e., systolic 140-159 or diastolic 90-99 mm Hg)	 *		
The patient has a close relative (e.g., parent or sibling) who has had a thromboembolic event at a young age (e.g., before 50)	 *		
History of renal calculus (kidney stone)			
Patient or someone in her immediate family has dyslipidemia	 *		
History of migraines	 *		
A cardiovascular condition such as atrial fibrillation, arrhythmia, coronary heart disease, cardiac valve disease	 *		
Diabetes mellitus	 *		
Chronic lassitude			
Practicing sports under no medical supervision			
Given birth in the last few weeks	 *		
Medical conditions that might increase the risk of thrombosis (e.g., cancer, systemic lupus erythematosus, sickle cell disease, Crohn's disease, ulcerative colitis, haemolytic uraemic syndrome)	 *		
Use of other medicines that can increase the risk of thrombosis (e.g., corticosteroids, neuroleptics, antipsychotics, antidepressants, chemotherapy)	 *		

Q16. What is the prescribing guidance on the use of Diane-35 or its generics for women who smoke?

Tick Yes, No, or I don't know for each prescribing guidance.

Prescribing Guidance	Yes	No	I don't know
Women who are greater than 35 years of age should strongly be advised to stop smoking or use a non-hormonal treatment for her acne and/or hirsutism	 *		
Women who are greater than 35 years of age and			

smoke can be prescribed Diane-35 and should be warned about potential risks of thrombosis			
Women of any age don't need to be advised to stop smoking if they smoke less than 5 cigarettes a day			

**Q17. Which medical conditions can increase the risk of thrombosis?
Tick Yes, No, or I don't know for each medical condition listed.**

Medical Condition	Yes	No	I don't know
Cancer	 *		
Diabetes mellitus	 *		
Systemic lupus erythematosus	 *		
Haemolytic uraemic syndrome	 *		
Urinary tract infection			
Chronic inflammatory bowel disease (e.g., Crohn's disease or ulcerative colitis)	 *		
Asthma			
Sickle cell disease	 *		

**Q18. A patient should be advised to seek immediate medical attention for which of the following symptoms of a possible deep vein thrombosis?
Tick Yes, No, or I don't know for each symptom listed.**

Symptoms	Yes	No	I don't know
Severe pain in a leg	 *		
Swelling in a leg	 *		
Skin rash on leg			
Changes in skin colour (e.g., pale, red, or blue) in a leg	 *		
Feeling of tenderness or warmth in a leg	 *		
A headache that has been lasting for more than a week			
Insomnia			

Q19. A patient should be advised to seek immediate medical attention for which of the following symptoms of a possible pulmonary embolism? Tick Yes, No, or I don't know for each symptom listed.

Symptoms	Yes	No	I don't know
Sudden unexplained breathlessness or rapid breathing	 *		
Chronic fatigue			
Severe pain in the chest which may increase with deep breathing	 *		
Sudden cough without an obvious cause (which may bring up blood)	 *		
A tingling or burning sensation limited to the left hand fingers			

Q20. A patient should be advised to seek immediate medical attention for which of the following symptoms of a possible myocardial infarction? Tick Yes, No, or I don't know for each symptom listed.

Symptoms	Yes	No	I don't know
Chest pain (often acute)	 *		
Chest discomfort, pressure, or heaviness	 *		
Upper body discomfort radiating to the back, jaw, throat, and arm together with a feeling of fullness associated with indigestion or choking	 *		
Sweating	 *		
Insomnia that started in the previous month			
Nausea or vomiting	 *		
Dizziness	 *		

Q21. A patient should be advised to seek immediate medical attention for which of the following symptoms of a possible cerebrovascular accident? Tick Yes, No, or I don't know for each symptom listed.

Symptoms	Yes	No	I don't know
Weakness or numbness of the face, arm, or leg, especially on one side of the body	 *		
Trouble speaking or understanding	 *		
A gradually increasing memory loss over the past year			
Sudden confusion	 *		

Sudden loss of vision or blurred vision	 *		
Hearing loss that has been increasing over the past year			
Severe headache/migraine that is worse than normal	 *		

The following questions ask about information you have received about Diane-35 or its generics.

Q22. Which of the following material(s) have you received?

Tick **all** that apply.

- Dear Healthcare Provider Letter for Diane-35 and/or its generics
- Diane-35 Patient Card
- Diane-35 Prescriber Checklist
- Other [PROGRAMMING NOTE: SKIP TO Q24]
- None of the above [PROGRAMMING NOTE: SKIP TO Q24]

[PROGRAMMING NOTE: ONLY DISPLAY RESPONSES THAT WERE TICKED IN Q22]

Q23. How helpful were these materials to you in treating and educating your patients?

Materials	Not at all helpful 1	2	3	Extremely helpful 4
Dear Healthcare Provider Letter for Diane-35 and/or its generics				
Diane-35 Patient Card				
Diane-35 Prescriber Checklist				

Q24. In the past 3 months, for how many total patients have you prescribed Diane-35 for the treatment of acne or hirsutism?

- None
- 1 to 3 patients
- 4 to 6 patients
- 7 to 10 patients
- 11 to 15 patients
- More than 15 patients
- I'm not sure

Thank you for completing the questionnaire!

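### The stem of question Q8 states as fact that the listed uses are indications, although the study's own key marks three of the five as not indicated

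*Protocol*

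**What the plan says.** Protocol, Annex 3, Physician Questionnaire, question Q8 opens with "Diane-35 and its generics are indicated for the following purposes. Tick Yes, No, or I don't know for each purpose listed". Five purposes follow. The annotated key marks Yes for moderate to severe acne and for hirsutism. It marks No for mild acne, for the row "For contraception only" and for androgenic alopecia. The key agrees with the indication printed in the patient card and the prescriber checklist in the same annex: "Treatment of moderate to severe acne related to androgen sensitivity (with or without seborrhoea) and/or hirsutism, in women of reproductive age".

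Other items in the instrument are put as questions. Q14, for example, asks: "Diane-35 and its generics are contraindicated in which of the following patient populations".

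Four design features bear on the point:
- Section 9.3 lists the approved indication as a content area of the questionnaire.
- Section 9.6.1 does not let respondents go back and change an answer, and it offers a telephone interview as an alternative to the web form.
- Section 9.7 analyses each question individually.
- Section 9.4.1 reports cognitive pretesting with 25 physicians, which covered question stems, but gives no item-level result.

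**The concern.** A respondent who takes the first sentence of Q8 at face value has been told that all five uses are approved, and the natural tick is then Yes. The study's key contradicts that sentence for three rows. Those rows matter most after a change of indication, because they are the ones that would show a belief in a use outside it.

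If the wording moves answers, the reported percentages partly reflect the stem and not what physicians took from the educational material. A larger sample would not correct this. Because items are reported one by one and answers cannot be revised, a misreading would go straight into the reported figure. By telephone the stem may be heard and not read, which makes it harder to set against the rows.

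**Working it through.** **Step 1: stem against key.** Q8 has five rows, two keyed Yes and three keyed No. The stem, read as a sentence, is true for 2 of 5 rows and false for 3 of 5. The key itself is sound, since it matches the printed indication.

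**Step 2: the plan's own precision figure.** Section 9.5 gives exact two-sided 95% limits of 81.6% to 88.0% for 85% correct at n=500. Clopper-Pearson limits for 425 of 500 reproduce this, as they do all 16 rows of Table 1. The half-width is (88.0 − 81.6)/2 = 3.2 points. This figure is not in dispute and serves only as a yardstick.

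**Step 3: what a pull towards Yes would do.** Two inputs are assumptions: k = 85% would answer a row correctly under a neutral stem, and a share s ticks Yes because of the stem whatever they know. The value of k follows the protocol's example. No document gives s.
- False row, percentage correct = k(1 − s)
- True row, percentage correct = k + (1 − k)s
- Mean of the five rows = (2 × true + 3 × false)/5

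| s | False rows | True rows | Mean of five rows |
|---|---|---|---|
| 0% | 85.0% | 85.0% | 85.0% |
| 2% | 83.3% | 85.3% | 84.1% |
| 5% | 80.8% | 85.8% | 82.7% |
| 10% | 76.5% | 86.5% | 80.5% |
| 20% | 68.0% | 88.0% | 76.0% |

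A false row reaches the planned lower limit when 85(1 − s) = 81.6, that is at s = 1 − 81.6/85 = 4%. A true row reaches the upper limit only when 85 + 15s = 88, that is at s = 20%.

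**Step 4: how far this depends on the model.** If only physicians who do not know the answer follow the stem, the false rows stay at 85.0%, because those physicians were not correct anyway. Only the true rows rise. At s = 0 nothing moves.

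**The case against.** The best defence is that Q8 does not leave its assertion standing. The second sentence asks for Yes, No or I don't know on each row, so a careful reader will see that the rows must be told apart. Mild acne and moderate to severe acne are separate rows with the distinguishing words underlined. Q9 also puts a declarative sentence to the respondent, to be judged true or false. The pretest in local languages looked specifically for problems with stems. All of this reduces the risk, but it does not remove it. In Q9 the sentence is itself what is judged, whereas in Q8 it precedes the rows and answers them. No pretest result for Q8 is reported.

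A reader might infer that Q11, Q15 and Q18 to Q21 have the same fault, because they call every row a risk factor or a symptom. The documents do not support that. These are questions about which rows apply, such as "Which of the following risk factors for the development of thrombosis should be considered prior to prescribing Diane-35 and its generics" and "A patient should be advised to seek immediate medical attention for which of the following symptoms of a possible deep vein thrombosis". They presuppose a label but do not assert the answer. In Q15 and Q18 to Q21 the label does sit on 11 un-keyed rows of 41 (3 + 3 + 2 + 1 + 2), so neutral labels would be tidier, but that is a minor matter.

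Q11 falls outside the point altogether. It asks when "the risk of a thrombosis is highest with which of the following risk factors", so a row can be a risk factor and still properly be answered No. One of its two un-keyed rows, family history of hypertension and/or dyslipidaemia, overlaps a family-lipids entry in the prescriber checklist and a row keyed Yes in Q15.

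**Conclusion.** Q8 has a leading stem: it is worded as a fact and is false for three of its five rows by the study's own key. That can be read directly from Annex 3 and rests on no assumption. The consequence is a risk of too many Yes answers on the item that tests which uses are approved. The likely direction is down on false rows and up on true rows.

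The size is unknown and may be zero. The table above is conditional on k = 85% and on a share s that no document supplies. A reader might conclude that the questionnaire is shown to bias measured knowledge, but the documents contain no evidence of that. At s = 5% the mean of the five Q8 rows moves by only about 2.3 points, inside the 3.2-point half-width, although a single false row falls below the planned lower limit. The point justifies correcting one stem. It does not call the rest of the instrument into question.

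**What to change.** Before fielding starts in any country, reword the Q8 stem as a neutral question, for example *For which of the following purposes are Diane-35 and its generics indicated?* Keep the row-by-row answering instruction, the five rows and the key unchanged. Use the same wording in all five countries and in both web and telephone modes, because a change partway through would make countries non-comparable.

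The cost is retranslation and reprogramming of one stem and an IRB notification. The new wording will not have been through the cognitive pretest. It adds no length and needs no extra physicians.

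Optional and minor: in Q15 and Q18 to Q21, replace the risk-factor and symptom labels with neutral ones. This has to be done in the stem, the instruction line and the column heading together, since all three carry the label. Q11 needs no change on this ground.

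### Q14 keys unqualified dyslipidemia as a contraindication, while the prescriber checklist it tests contraindicates only very high blood lipids (minor)

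*Protocol*

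**What the plan says.** The introduction to the Physician Questionnaire (Protocol, Annex 3) states its purpose: "This questionnaire will be used to determine if the educational materials for Diane-35 and its generics are understood accurately". Section 8 names contraindications relevant to thromboembolism as a knowledge area, and Q14 is the question that lists contraindicated populations. One of its rows is "Patients with dyslipidemia", with the asterisk in the Yes column.

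The Prescribers' Checklist, also in Annex 3, treats lipids in two tiers. The do-not-prescribe box has "Very high blood lipids". The box of factors to be discussed with the woman has "Does she or someone in her immediate family have high blood lipids".

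Section 9.3 says that the version in Annex 3 is the final questionnaire. The wording and the key are therefore fixed in this document and are not left to the analysis plan.

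**The concern.** A knowledge item should be keyed to the material whose understanding it tests. Here the keyed statement is broader than the rule in the checklist. A physician who knows that only very high lipids rule the drug out, and that lesser elevations call for a discussion, has no row in Q14 that states that rule. Faced with dyslipidemia in general, such a physician may answer No and be recorded as not matching the key.

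What is at stake is the interpretation of one reported percentage. A low figure for this row could mean that physicians do not know the contraindication, or that they know it more exactly than the row allows. The reported figure would not show which. More respondents would narrow the interval around that percentage without resolving the ambiguity.

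**Working it through.** **The plan's own figures.** The only design figures are the exact confidence limits in Table 1 (section 9.5). For 500 physicians and 85% correct, x = 425, and the Clopper-Pearson limits are 81.6% and 88.0%, as printed. All 16 rows of the table reproduce to one decimal. None of them depends on the wording of Q14.

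**Reading the asterisk.** The supplied text has no legend. In Q9 the asterisk stands on True, which is the answer that agrees with the approved indication, and the starred rows elsewhere in Q14 fit the same reading. I take it as the keyed answer.

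**Checklist against Q14.** The checklist splits four conditions between its two boxes:

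| Condition | Do-not-prescribe box | Discuss box | Q14 row, keyed Yes |
|---|---|---|---|
| Blood pressure | very high, with ≥160 or ≥100 mm Hg as example | "Does she have high blood pressure eg systolic 140-159 or diastolic 90-99mm Hg" | opens "Patients with hypertension (e.g., systolic" and goes on to give ≥160 or ≥100 |
| Migraine | with aura | "Does she get migraines" | "Patients with a history of migraine with aura" |
| Diabetes | with vascular complications | diabetes in general | with vascular complications |
| Blood lipids | "Very high blood lipids" | "Does she or someone in her immediate family have high blood lipids" | "Patients with dyslipidemia" |

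For the first three conditions, the Q14 row carries something that points to the upper tier. The lipid row carries nothing, so as worded it covers both tiers. I found no other text in the protocol that makes dyslipidemia in general a contraindication.

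**Reach.**
- Q14 has 11 rows, so the lipid row is 1/11 = 9.1% of them. Nine are keyed Yes (all but childhood asthma and moderate anaemia), so it is 1/9 = 11.1% of those.
- Rows in Q8 to Q21: 5 + 1 + 3 + 6 + 5 + 6 + 11 + 15 + 3 + 8 + 7 + 5 + 7 + 7 = 89. The lipid row is 1/89 = 1.1%.
- The checklist's do-not-prescribe box has 8 entries, of which lipids are 1/8 = 12.5%.

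**Size of the effect.** Let k be the share of physicians who know the two-tier rule and q the share of those who answer No because the row is unqualified. The row then loses k × q from its percentage correct. The protocol gives neither k nor q. With q = 0, if everyone reads the row as including very high lipids, the loss is nil. With q = 1 it is k. No figure between can be defended from the documents.

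**The case against.** Several objections carry some weight.

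- **Very high lipids are a form of dyslipidemia, so Yes is defensible.** This stands in part. A reader might infer that the key is reversed, or flatly contradicts the checklist. It does not: the row is too broad. Many physicians may match the key without difficulty, which is why the size is unknown.
- **The contrast with blood pressure is less sharp than it looks.** The Q14 hypertension row also drops the words for very high and gives its numbers only as an example. That is true, but the numbers still identify the upper tier, and the lipid row has no such cue.
- **A Yes cannot separate accurate from over-general knowledge.** A reader might add this to the case. It does not belong there. A Yes to the migraine-with-aura row has the same weakness, and so would a Yes to the reworded lipid row. The specific harm is confined to the informed No.
- **Q15 uses the same term for the lower tier.** A reader might see a contradiction between the two questions. There is none, because Q15 asks what to consider before prescribing, and a contraindication must be considered too.
- **Scoring belongs to the analysis plan, and the questionnaire was pretested and had an approval step.** Section 9.7 is descriptive, and the protocol sets no pass mark, so how the row is presented is indeed for the analysis plan. That plan cannot restore a qualifier missing from the question. The pretest with 25 physicians (section 9.4.1) is described as a check on how items are understood, not on whether the key agrees with the checklist.

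**Conclusion.** The point holds as a minor error in the text as written. The Q14 lipid row is keyed to a broader statement than the checklist makes, and its percentage correct will not cleanly measure knowledge of this contraindication.

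The conclusion rests on reading the asterisk as the keyed answer and on the checklist as the standard. The checklist gives no numeric lipid cut-off, and the Summary of Product Characteristics is not available here, so nothing is said about agreement with it.

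Two wider conclusions are not supported. The first is that the survey's overall finding on contraindications is unreliable: one row of 11 in Q14, with an effect of unknown size, does not show that, and the sample size and precision are untouched. The second is that the remaining rows have been checked and found sound, or unsound. The comparison covers the four tiered conditions, and no claim is made about other rows.

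**What to change.** Reword the Q14 row to ask about patients with very high blood lipids, which is the checklist's own term, and keep Yes as the keyed answer. The cost is retranslation of one row into the local-language versions and probably a minor amendment, since section 6 lists regulatory approval of the questionnaire (August 2014) and section 10 has the institutional review board review it. Timing matters: under section 6, collection in Austria, the Czech Republic and the Netherlands may start after that board's approval (April 2015), before France and Spain.

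If the questionnaire is already in the field, leave the wording as it is in all five countries. Report the row's split between Yes, No and I don't know, footnote the missing severity qualifier, and do not interpret a No as a clear failure of knowledge. This has no field cost. The row need not be dropped from the results.
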